4.1 Treatment beyond progression

The local investigator may choose to continue treatment with osimertinib beyond RECIST 1.1 PD, if, in their opinion, the patient continues to receive clinical benefit. However, this should be discussed with the EORTC HQ. Information on post-PD treatment needs to be provided to EORTC HQ and follow-up must follow chapter 6 according to the treatment arm.

In case of oligo-progressive disease (please refer to chapter 0) in a known metastatic lesion local therapy (radiotherapy / surgery / cryotherapy) will be allowed after mandatory discussion with EORTC headquarters. This procedure will be reported in the CRF. Information on post-PD treatment needs to be provided to EORTC HQ and follow-up must follow chapter 6 according to the treatment arm.

5 Therapeutic regimens, expected toxicity, dose modifications

Osimertinib (AZD9291) and gefitinib are considered as Investigational Medicinal Products.

5.1 Osimertinib

5.1.1 General information

DrugBank number: DM09330

Other names: AZD9291
Trade name: Tagrisso
Molecular weight: 499.62

Description: orally taken, beige, filmcoated tablet containing 40 mg or 80 mg of osimertinib expressed as free base (equivalent of 47.7 mg or 95.4 mg of osimertinib mesalate).

Osimertinib (TAGRISSO $^{\mathbb{N}}$ 1, laboratory code AZD9291) is an oral, irreversible inhibitor of the tyrosine kinase activity of the epidermal growth factor receptor activating mutation (EGFRm) and the resistance mutation (T790M) specifically.

For more general information related to osimertinib please refer to the latest version of the Investigator Brochure.

5.1.2 Drug supply

Drug supplies and re-supplies will be provided free of charge by drug guidelines that will be provided at the time of activation).

The osimertinib drug product is provided in the high-density polyethylene bottles, 35 tablets per bottle.

All instructions pertaining to drug management and drug supply can be found in the study drug guidelines (provided as a separate document).

5.1.3 Packaging, dispensing and storage

Drug labels will comply with good manufacturing practice (GMP) and will be printed in the national language. The storage conditions for study drug will be described on the medication label.

Osimertinib must be stored at room temperature (between 15-30°C or 59-86°F).

Osimertinib tablets should not be used beyond the expiration date provided by the manufacturer.

Study drug will be prepared and dispensed by the pharmacist at the investigator's institution. The pharmacy must maintain an individual record for the patient.

The clinical trial centers will keep a trial specific authorization list which determines the persons responsible for handling of the investigational drugs. The responsible person will follow the standard practice and directive (Annex 13).

For more information regarding the packaging, storage and dispensing of osimertinib please refer to the latest version of the Investigator Brochure and the drug guidelines.

5.1.4 Drug reconciliation procedures

Accountability of the investigational study drug(s) is under the responsibility of the investigator and can be delegated to an appropriately qualified person.

Study drug accountability should be maintained by each site.

In addition to internal accountability documentation on site, EORTC study-specific accountability and drug destruction forms will be supplied for this purpose, if site-specific forms are deemed not sufficiently detailed or do not provide enough information, according to EORTC Quality Assurance criteria.

The drug accountability and destruction forms will be verified during monitoring visits.

At the end of study, when all patients have stopped protocol treatment, complete drug reconciliation per batch should be available at the site for verification by EORTC in order to allow drug destruction or return procedure.

Both the unused and expired study medication must be destroyed, upon authorization of the sponsor, according to local regulations and procedures, and a copy of the destruction form must be returned to the EORTC HQ.

The medication provided for this trial is to be used only as indicated in this protocol and only for the patients entered in this study.

5.2 Gefitinib

5.2.1 General information

DrugBank number: DM00317

Other names: ZD1839

Trade name: IRESSA 250

Molecular weight: 446.90

Description: orally taken, brown, round, biconvex tablets containing 250 mg of gefitinib

Gefitinib (IRESSA[™], laboratory code) is an oral, reversible inhibitor of the tyrosine kinase activity of the epidermal growth factor receptor activating mutation (EGFRm).

For more general information related to gefitinib please refer to the latest version of the Summary of Product Characteristics (SmPC).

5.2.2 Drug supply

Drug supplies and re-supplies will be provided free of charge by drug guidelines that will be provided at the time of activation).

Gefitinib is provided in in the high-density polyethylene bottles, 30 tablets per bottle.

All instructions pertaining to drug management can be found in the study drug guidelines (provided as a separate document).

For more information regarding the supply of gefitinib please refer to the latest version of the SmPC.

5.2.3 Packaging, dispensing and storage

Drug labels will comply with the good manufacturing practice (GMP) and will be printed in the national language. The storage conditions for study drug will be described on the medication label.

Gefitinib must be stored at room temperature (between 15-30°C or 59-86°F).

Gefitinib tablets should not be used beyond the expiration date provided by the manufacturer.

Study drug will be prepared and dispensed by the pharmacist at the investigator's institution. The pharmacy must maintain an individual record for the patient.

The clinical trial centers will keep a trial specific authorization list which determines the persons responsible for handling of the investigational drugs. The responsible person will follow the standard practice and directive (Annex 13).

For more information regarding the packaging, storage and dispensing of gefitinib please refer to the latest version of the SmPC.

5.2.4 Drug reconciliation procedures

Accountability of the investigational study drug(s) is under the responsibility of the investigator and can be delegated to an appropriately qualified person.

Study drug accountability should be maintained by each site.

In addition to internal accountability documentation on site, EORTC study-specific accountability and drug destruction forms will be supplied for this purpose, if site-specific forms are deemed not sufficiently detailed or do not provide enough information, according to EORTC Quality Assurance criteria.

The drug accountability and destruction forms will be verified during monitoring visits.

At the end of study, when all patients have stopped protocol treatment, complete drug reconciliation per batch should be available at the site for verification by EORTC in order to allow drug destruction or return procedure.

Both the unused and expired study medication must be destroyed, upon authorization of the sponsor, according to local regulations and procedures, and a copy of the destruction form must be returned to the EORTC HQ.

The medication provided for this trial is to be used only as indicated in this protocol and only for the patients entered in this study.

5.3 Initial dose and schedule

Advanced EGFR mutant NSCLC and EGFR-TKI naïve patients, will be randomized to:

- Arm A: osimertinib 80 mg QD until RECIST 1.1 progression.
- Arm B: gefitinib 250mg QD until cfDNA T790M positive test (criteria for defining progression disease), irrespective of RECIST 1.1 criteria, then patients will receive osimertinib 80 mg QD until RECIST 1.1 progression. If patients have RECIST 1.1 progression without cfDNA T790M positive test, they will be switched to osimertinib.
- Arm C: gefitinib 250mg QD until RECIST 1.1 progression, irrespective of cfDNA T790M test, then patients will receive osimertinib 80 mg QD until RECIST 1.1 progression.

Continuation of osimertinib post-PD is allowed on individual basis provided that in the opinion of treating physician, patient may benefit from this therapy (please refer also to section 4.1).

Osimertinib or gefitinib must be swallowed with a glass of water and must not be mashed or chewed. The tablets can be taken preferably in the morning with or without meals

The initial dose of osimertinib 80 mg once daily can be reduced to 40 mg once daily. The initial dose for gefitinib (250 mg once daily) cannot be reduced to a lower dose.

5.4 Treatment duration

- In ARM A (osimertinib): Treatment should be administered until documented disease progression by RECIST 1.1 criteria, unacceptable toxicity, or patient refusal. Continuation of osimertinib post-PD is allowed on individual basis provided that in the opinion of treating physician, patient may benefit from this therapy.
- In ARM B (gefitinib): Treatment should be administered until RECIST 1.1 progression at which point
 osimertinib will be started. In case of unacceptable toxicity to any of both drugs or patient refusal,
 treatment can be discontinued. Continuation of osimertinib post-PD is allowed on individual basis
 provided that in the opinion of treating physician, patient may benefit from this therapy.
- In ARM C (gefitinib): Treatment should be administered until documented disease progression by RECIST 1.1 criteria, unacceptable toxicity, or patient refusal. Then patients will receive osimertinib until RECIST 1.1 progression. In case of unacceptable toxicity to any of both drugs or patient refusal, treatment can be discontinued. Continuation of osimertinib post-PD is allowed on individual basis provided that in the opinion of treating physician, patient may benefit from this therapy.

5.5 Withdrawal criteria

Whatever the disease status, the treatment will always be discontinued in case of

- AE or intercurrent illness that, in the opinion of the investigator, warrants the patient's withdrawal from study treatment;
- Patient refusal or lost to follow-up;
- Excessive toxicity precluding further therapy, according to the responsible physician;
- Any adverse events specified as a reason for permanent discontinuation as defined in the guidelines for dose modification due to AE in section 5.6 and subsections

- Significant non-compliance/non-adherence with the protocol schedule in the opinion of the investigator or the sponsor;
- PD according to RECIST 1.1 to osimertinib; continuation of osimertinib post-PD is allowed on individual basis provided that in the opinion of treating physician, patient may benefit from this therapy;
- Pregnancy;
- Start of a new anticancer treatment.

Patients discontinuing therapy not according to the protocol should not receive any other cancer treatment before their disease progresses, unless this is clearly not in the interest of the patient according to the local investigator.

After progression to osimertinib, the treatment will be left to the discretion of the treating physician. Any anti-cancer therapy other than the study drug given as single agent will not be considered as part of the protocol treatment.

5.6 Dose and schedule modifications

Dose modifications are required only for toxicities that are not considered to the disease or disease-related processes under investigation. Dose modifications are not required for events that are not considered clinically significant such as isolated laboratory abnormalities, alopecia.

Note: Persistent grade 1 AE, lasting longer than 10 days under appropriate treatment, should be considered and treated as a grade 2 event.

5.6.1 Osimertinib

All patients start treatment with osimertinib at 80 mg daily irrespective if the patient received osimertinib as first-line treatment or as sequential treatment after gefitinib. Only 1 dose reduction with osimertinib (to 40 mg) will be allowed during the study.

If a patient experiences a CTCAE grade 3 or higher and/or unacceptable toxicity (any grade) not attributable to the disease or disease-related processes under investigation, where the Investigator considers the AE of concern to be specifically associated with the study drug dosing will be interrupted and supportive therapy administered as required in accordance with local practice/guidelines.

If the toxicity resolves or reverts to ≤CTCAE grade 2 within 3 weeks of onset, study drug may be restarted at the same dose (starting dose) or a lower dose (40 mg) using the rules below for dose modification (Table "Recommended dose modifications with osimertinib). There will be no individual modifications to dosing schedule in response to toxicity, only potential dose reduction or dose interruption. If restarting at the same dose level, patients should be closely monitored for 3 days following the restart of treatment. If within 3 days there is recurrence of same toxicity, a dose reduction should be considered at the Investigator's discretion.

If the toxicity does not resolve to ≤CTCAE grade 2 after 3 weeks of withholding osimertinib, then the patient should be withdrawn from the study treatment and observed until resolution of the toxicity. There will be no individual modifications to treatment schedule in response to toxicity, only potential dose reduction or dose interruption.

If an AE subsequently requires dose interruption, study drug may restart at the same dose or the reduced dose, on resolution/improvement of the AE at the discretion of the investigator as described above.

Recommended dose modifications with osimertinib

Target Organ	Adverse reaction	Modification
Pulmonary	Interstitial lung disease (ILD)/Pneumonitis	Permanently discontinue osimertinib
Cardiac	QTc† interval greater than 500 msec on at least 2 separate ECGsb	Withhold osimertinib until QTc interval is less than 481 msec or recovery to baseline if baseline QTc is greater than or equal to 481 msec within 3 weeks of withholding osimertinib, then resume at 40 mg dose or at 80 mg (at the discretion of the investigator, to allow for situations where causality in relation to osimertinib may be difficult to determine)
	QTc interval prolongation with signs/symptoms of serious arrhythmia	Permanently discontinue osimertinib
	Asymptomatic, absolute decrease in LVEFc of 10% from baseline and below 50%	 Withhold osimertinib for up to 2 weeks. If improved to baseline LVEF, resume. If not improved to baseline, permanently discontinue.
	Symptomatic congestive heart failure	Permanently discontinue osimertinib
Other	Grade 3 or higher adverse reaction	Withhold osimertinib for up to 3 weeks
	If improvement to Grade 1 within 3 weeks	Resume at 80 mg or 40 mg daily
	If no improvement to Grade1 within 3 weeks	Permanently discontinue osimertinib

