5.6.1.2 QTc prolongation

In light of the potential for QT changes associated with osimertinib, electrolyte abnormalities (hypokalemia, hypomagnesaemia, hypocalcemia) must be corrected to be within normal ranges prior to first dose and electrolyte levels monitored during study treatment.

Patients with QTcF prolongation to >500 msec should have study treatment interrupted and regular ECGs performed until resolution to <481 msec or recovery to baseline if baseline QTcF is >481 msec and then restarted at a reduced dose of 40 mg, or 80mg at the discretion of the investigator. If the toxicity does not resolve to \leq grade 1 within 21 days of withholding osimertinib the patient will be permanently withdrawn from study treatment.

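### After a grade 3 or higher osimertinib toxicity that has fallen to grade 2 at 3 weeks, the text of section 5.6.1 allows restart while its table requires permanent discontinuation

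*Combined protocol and SAP*

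**What the plan says.** Section 5.6.1 opens with the trigger for interrupting osimertinib: "If a patient experiences a CTCAE grade 3 or higher and/or unacceptable toxicity (any grade) not attributable to the disease", where the investigator attributes the event to study drug. Two sentences then decide what follows.

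- Restart: "If the toxicity resolves or reverts to ≤CTCAE grade 2 within 3 weeks of onset, study drug may be restarted at the same dose" or at the reduced dose. This sentence refers the reader to the dose-modification table.
- Withdrawal: "If the toxicity does not resolve to ≤CTCAE grade 2 after 3 weeks of withholding osimertinib, then the patient should be withdrawn" from study treatment. This sentence does not mention the table.

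The table in the same section has separate rows for lung, QTc, LVEF and heart-failure events, and a general category, Other. In that category the trigger is "Grade 3 or higher adverse reaction", and the drug is withheld for up to 3 weeks. Treatment resumes if the event improves to grade 1. The last row, "If no improvement to Grade1 within 3 weeks", leads to permanent discontinuation.

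Section 5.5 adds that treatment is always discontinued for adverse events that section 5.6 names as grounds for permanent discontinuation.

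Section 5.6.1.2, which covers QTc only, applies a third form: without resolution to "grade 1 within 21 days of withholding osimertinib the patient will be permanently withdrawn from study treatment".

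**The concern.** The text and the table govern one decision for one trigger, yet they set different recovery grades. A patient whose toxicity has improved from grade 3 or higher to grade 2 at 3 weeks falls between them.

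The first consequence is for patients. A site reading the text could re-expose someone whom the table says must stop. A site reading the table would withdraw someone whom the text allows to continue. Osimertinib is planned treatment in all three arms (section 5.3), so no arm is exempt.

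The second consequence is for the data. Treatment duration is a secondary endpoint (section 7.2.7). Interruptions, dose modifications and compliance with the 70% dose-intensity requirement are monitored safety parameters (section 7.3.5). Each would partly reflect which passage a site followed, and nothing in the analysis plan would separate that from tolerability.

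**Working it through.** The plan states no figure to reproduce here. The check sets the two rules side by side for a grade 3 or higher event in the table's general category.

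| Grade at 3 weeks | 5.6.1 text | 5.6.1 table | Agree? |
|---|---|---|---|
| 0-1 | Restart permitted | Resume | Yes |
| 2 | Restart permitted | Permanently discontinue | **No** |
| 3 or higher | Withdraw | Permanently discontinue | Yes |

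The rules conflict at grade 2 and nowhere else. The text states the grade 2 threshold in two sentences and the table states grade 1 in two rows, so a misprint or a reading error is unlikely.

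**Grade boundary.** A note in section 5.6 says that a grade 1 event persisting beyond 10 days under treatment is to be handled as grade 2. Under the table's threshold, that leaves even a grade 1 patient's status open to interpretation.

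**Clock.** The text measures restart from onset and withdrawal from the start of withholding. If dosing stops *d* days after onset, the restart window closes on day 21 after onset and the withdrawal rule applies on day 21 + *d*. With an assumed *d* = 7, a patient who recovers to grade 2 between days 22 and 28 after onset meets neither sentence.

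**Illustrative size.** Inputs:
- Section 1.3 reports grade 3 or higher events in 29.4% of patients in the phase II studies, and 11.7% considered related to osimertinib.
- Planned accrual is 156, or 52 per arm (section 8.1.1).

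Patients entering the rule:
- All 156 receive osimertinib: 0.117 × 156 = 18.3.
- Only arm A receives it (lower extreme): 0.117 × 52 = 6.1.

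The documents do not give the share at grade 2 at 3 weeks. At an assumed 20-50%:
- From 18.3: 0.20 × 18.3 = 3.7 to 0.50 × 18.3 = 9.1 patients.
- From 6.1: 0.20 × 6.1 = 1.2 to 0.50 × 6.1 = 3.0 patients.

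These figures read 11.7% as a share of patients, which fits the 11% of treatment-related grade 3 or higher events that section 1.3 gives for one of the phase II studies. If it were a share of the 29.4%, the count would be 0.117 × 0.294 × 156 = 5.4 patients entering the rule.

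**The case against.** The strongest reply is that the two passages can be obeyed together. The text only permits restart, and it points to the table when doing so. Section 5.5 makes the table's discontinuation row mandatory. On that reading a site that follows the table breaches nothing, and the defect is a permission that other passages do not honour. This narrows the problem but does not remove it. The text grants restart at grade 2 and then points to a table that excludes it. The withdrawal sentence repeats grade 2 without any reference to the table. The table is headed as recommended modifications, and no passage says which prevails. A site relying on the text alone would restart in good faith.

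Three further points stand:
- Section 5.6.1.2 is specific to QTc, which has its own table row. A specific rule that differs from a general one is not in itself a contradiction, so it is context rather than the core of the conflict.
- The count of 18 is an upper bound. Some patients in arms B and C may never start osimertinib (section 7.2.2 provides for this), and the 11.7% includes events that have their own table rows.
- The primary analysis is largely protected. PFS-OSI is used regardless of treatment discontinuation, with imaging continued (section 7.2.2), and toxicity is not formally compared between arms (section 8.2.2).

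**Conclusion.** The contradiction is real and lies wholly in current text. For a grade 3 or higher reaction in the table's general category that stands at grade 2 at 3 weeks, the text permits restart, while the table, backed by section 5.5, requires permanent discontinuation. The mismatch between onset and withholding clocks is a second, smaller defect.

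The number affected is uncertain: at most about 18 patients enter the rule, and about 4 to 9 of them reach the disputed grade if 20-50% are at grade 2 at 3 weeks. That share is an assumption, and the finding does not depend on it. The sample size and the requirement of 25 successes in 49 patients do not change. The case for a mandatory correction rests on patient safety and on the interpretability of discontinuation, dose-modification and treatment-duration data.

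**What to change.** Reconcile the section 5.6.1 text, its table and section 5.6.1.2, with section 5.5 in view, so that each toxicity has one recovery grade and one clock, stated as running from onset or from withholding. State which passage prevails if a general and a specific rule both apply, and whether the section 5.6 note on persistent grade 1 events applies to recovery. The clinical team must choose the threshold; this review takes no position on it.

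The cost is a protocol clarification sent to sites, with no effect on sample size or analysis. Optionally, record on the CRF which rule was applied to patients already managed under this section, so that their discontinuation data can be interpreted. That would add some retrospective data collection and is not essential to the correction.

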5.6.1.1 Interstitial Lung Disease (ILD)/pneumonitis like toxicity

If new or worsening pulmonary symptoms (e.g., dyspnea) or radiological abnormality suggestive of interstitial lung disease/pneumonitis is observed, an interruption in study treatment dosing is recommended, and the Sponsor study team should be informed.

It is strongly recommended to perform a full diagnostic workup, to exclude alternative causes such as lymphangitic carcinomatosis, infection, allergy, cardiogenic oedema or pulmonary hemorrhage. The results of full diagnostic workup (including high-resolution computed tomography (HRCT), blood and sputum culture, hematological parameters) will be captured by eCRF.

In the presence of confirmatory HRCT scans where other causes of respiratory symptoms have been excluded, a diagnosis of interstitial lung disease should be considered and study treatment permanently discontinued.

